2.2. Hypothesis

To demonstrate the non-inferiority of the concomitant administration of Ad26.RSV.preF and seasonal influenza vaccine versus the administration of seasonal influenza vaccine, 28 days after the administration of the seasonal influenza vaccine in terms of humoral immune response, the following hypothesis will be tested for each one of the four influenza vaccine strains:

Null Hypothesis:

- The GMT of HI antibody titers against one vaccine strain, 28 days after concomitant administration of Ad26.RSV.preF and seasonal influenza vaccine is inferior by at least 2 to the GMT 28 days after the administration of seasonal influenza vaccine

Alternative Hypothesis:

- The GMT of HI antibody titers against one vaccine strain, 28 days after concomitant administration of Ad26.RSV.preF and seasonal influenza vaccine is non-inferior to the GMT 28 days after the administration of seasonal influenza vaccine, using a non-inferiority margin of 2, for the ratio $GMT_{control\ group}/GMT_{co-administration\ group}$

No formal statistical testing of safety data is planned. All safety data will be analyzed descriptively by regimen.

3. STUDY DESIGN AND RATIONALE

3.1. Overview of Study Design

This is a single center, randomized, placebo-controlled, double-blind Phase 2a study, to be conducted in 180 adult male and female subjects aged ≥ 60 years of age in stable health randomized in parallel in a 1:1 ratio to one of two groups. Group 1 will receive 1×10^{11} vp Ad26.RSV.preF on Day 1 administered at the same time as a commercially available seasonal influenza vaccine, and placebo on Day 29. Group 2 will receive placebo on Day 1, administered at the same time as a commercially available seasonal influenza vaccine, and 1×10^{11} vp Ad26.RSV.preF on Day 29. All study vaccines will be given by the intramuscular route. An internal data review committee (DRC) will be commissioned for this study.

Table 4: Study Design

Group	N	Day 1	Day 29
1	90	Ad26.RSV.preF (1×10^{11} vp) + Fluarix	Placebo
2	90	Placebo + Fluarix	Ad26.RSV.preF (1×10^{11} vp)

N = number of subjects; vp = viral particles

After each vaccination, subjects will be closely observed for a minimum of 30 minutes post-vaccination to monitor for the development of any acute reactions, or longer if deemed necessary by the investigator. Any unsolicited, solicited local or systemic AEs will be documented by study-site personnel following this observation period. Subjects will be given a thermometer, ruler and daily assessment (subject) diary with instructions for the proper recording of events. Each subject will record solicited local (at injection site) and systemic AEs and body temperatures, beginning on the evening of each study vaccine dosing day and on a daily basis for the following 7 days. Body temperatures should be taken at approximately the same time each day. Study-site personnel will collect and review subject diary information and confirm the entries at subsequent site visits.

Unsolicited AEs will be collected from ICF signature through 28 days after the second vaccination. SAEs will be collected from ICF signature until the end of the study. All AEs, including any that are ongoing 28 days after the second vaccination, will be followed until clinical resolution or stabilization. Concomitant medications will be collected and recorded in the electronic case report form (eCRF) from the time of first vaccination through 28 days after the second vaccination, and additionally outside of this period when associated with an SAE.

Blood will be collected from all subjects to assess humoral immune responses pre-vaccination on each dosing day, and at 28 days after the second vaccination (or at the early exit visit if the subject prematurely terminates the study before Day 57 without withdrawing consent^a); cellular immune responses may be assessed at these timepoints in a subset containing 40 randomized subjects (ie, 20 per group).

^a Immunogenicity blood samples will only be taken if early exit is at least 14 days after the previous immunogenicity blood draw.

[figure not shown]
An independent unblinded statistician and unblinded biomarker representative will present data to the DRC if non-inferiority of the concomitant administration of influenza vaccine with Ad26.RSV.preF versus the administration of influenza vaccine alone is not demonstrated, based on the immunogenicity analysis at 28 days after the first dose. The DRC will decide if subjects should be offered repeat influenza immunization (see Section 11.6 for more details).

The study duration will be approximately 30 weeks per participant. The study comprises vaccination for each subject on Day 1 and Day 29, a 28-day follow-up period after each vaccination, and a follow-up until 6 months after the second vaccination. The end of the study will be the last subject's last visit by telephone at 6 months after the second vaccination.

If symptoms of an RTI develop from Day 1 through the end of the study, subjects should record signs and symptoms of the RTI using a specific RTI Symptoms Form and, if feasible, take a nasal turbinate sample. Details on procedures in the event of an RTI are described in Section 9.2.3.

Unscheduled study visits may be performed based on investigator's clinical judgment and may include further evaluations, as needed.

A diagram of the entire study design is provided in [Figure 1](#).

Figure 1: Schematic Overview of the Study

*by telephone

3.2. Study Design Rationale

Availability of Safety Data Prior to Dosing

Two initial FIH studies (VAC18192RSV1001, N = 48; VAC18192RSV1003, N = 32) in healthy adults examining homologous and heterologous regimens of 5×10^{10} vp of Ad26.RSV.FA2 and 5×10^{10} vp of Ad35.RSV.FA2 have been completed. Both Ad26.RSV.FA2 and Ad35.RSV.FA2 were shown to be safe and immunogenic.

One subsequent FIH study (VAC18193RSV1003, N = 72) in adults aged 60 years and older in stable health examining homologous regimens of 5×10^{10} vp and 1×10^{11} vp of Ad26.RSV.preF is ongoing. All 72 subjects have been randomized and have received the first dose. Safety data from the unblinded interim analysis 28 days post-Dose 1 from all 72 subjects who received Ad26.RSV.preF (5×10^{10} vp or 1×10^{11} vp) or placebo did not reveal any safety concerns.

Dose Selection

The rationale behind selection of the Ad26 vector and dose selection is described in Section 1.1.

Rationale for Vaccine Regimen Selection

Influenza vaccines are given yearly before the start of the season and it is likely that an RSV vaccine would be given at the same time. This study will examine the effect on the immunogenicity of both vaccines of giving a seasonal influenza vaccine and Ad26.RSV.preF at the same time and at separate times to provide an indication of whether these vaccines can be used concomitantly.

Thus, male and female subjects aged ≥ 60 years will be dosed with 1×10^{11} vp Ad26.RSV.preF at the same time as seasonal influenza vaccine on Day 1, and in the absence of seasonal influenza vaccine on Day 29.

4. SUBJECT POPULATION

The inclusion and exclusion criteria for enrolling subjects in this study are described in the following two subsections. If there is a question about the inclusion or exclusion criteria below, the investigator must consult with the appropriate sponsor representative and resolve any issues before enrolling a subject in the study. Waivers are not allowed.

Screening for eligible subjects will be performed pre-vaccination on Day 1.

4.1. Inclusion Criteria

Each potential subject must satisfy all of the following criteria to be enrolled in the study:

1. Each subject must sign an ICF indicating that he or she understands the purpose of and procedures required for the study, is willing to participate in the study and attend all scheduled visits, and is willing and able to comply with all study procedures and adhere to the prohibitions and restrictions specified in this protocol.
2. Subject must be a man or woman, ≥ 60 years old on the day of signing the ICF and available for the duration of the study.
3. Before randomization, a woman must be:
 - postmenopausal
A postmenopausal state is defined as no menses for 12 months without an alternative medical cause; and
 - not intending to conceive by any methods.
4. Criterion modified per Amendment 1:
 - 4.1 In the investigator's clinical judgment, subject must be either in good or stable health, and not at risk of serious complications from influenza. Subjects may have underlying illnesses such as hypertension, type 2 diabetes, hyperlipoproteinemia, or hypothyroidism, as long as their symptoms/signs are medically controlled. If they are on medication for a condition, the medication dose must have been stable for at least 12 weeks (or only small, clinically non-significant changes have been made in the judgement of the PI) preceding vaccination and expected to remain stable for the duration of the study. Subjects will be included on the basis of physical examination, medical history, vital signs, and 12-lead electrocardiogram (ECG)^a performed on Day 1.

^a Retesting of abnormal vital signs or ECG values that may lead to exclusion, or due to equipment malfunction, will be allowed once without prior approval from the sponsor.

5. From the time of first vaccination through 3 months after the second dose of study vaccine, subject agrees not to donate blood.
6. Subject must be willing to provide verifiable identification, have means to be contacted and to contact the investigator during the study.

4.2. Exclusion Criteria

Any potential subject who meets any of the following criteria will be excluded from participating in the study:

1. Subject has acute illness (this does not include minor illnesses such as diarrhea) or temperature $\geq 38.0^{\circ}\text{C}$ within 24 hours prior to the first dose of study vaccine; enrollment at a later date is permitted.
2. Subject has a serious chronic disorder, including severe chronic obstructive pulmonary disease or clinically significant congestive heart failure, requirement for supplemental oxygen, end stage renal disease with or without dialysis, clinically unstable cardiac disease, Alzheimer's disease, or has any condition for which, in the opinion of the investigator, participation would not be in the best interest of the subject (eg, compromise well-being) or that could prevent, limit, or confound the protocol-specified assessments.
3. Subject has history of malignancy within 5 years before screening (exceptions are squamous and basal cell carcinomas of the skin and carcinoma in situ of the cervix, or malignancy, which is considered cured with minimal risk of recurrence).
4. Subject has had major surgery (per the investigator's judgment), within 4 weeks before dosing, or will not have fully recovered from surgery, or has surgery planned during the time the subject is expected to participate in the study or within 6 months after the final dose of study vaccine. *Note:* Subjects with planned surgical procedures to be conducted under local or locoregional anesthesia and not judged as major by the investigator may participate.
5. Subject has chronic active hepatitis B or hepatitis C infection, documented by hepatitis B surface antigen and hepatitis C antibody, respectively.
6. Subject has HIV type 1 or type 2 infection.
7. Subject has had major psychiatric illness and/or drug or alcohol abuse which in the investigator's opinion would compromise the subject's safety and/or compliance with the study procedures.
8. Subject has a known allergy, or history of anaphylaxis or other serious adverse reactions to vaccines or vaccine components (including any of the constituents of the study vaccines).
9. Subjects with a history of allergy to egg protein.
10. Criterion modified per Amendment 1:
 - 10.1 Subject has a history of chronic urticaria (recurrent hives), eczema and/or atopic dermatitis. *Note:* Subjects with a history of eczema only in childhood are allowed.
11. Subject has a history of acute polyneuropathy (eg, Guillain-Barré syndrome).

12. Subject has abnormal function of the immune system resulting from:
 - Clinical conditions (eg, autoimmune disease or immunodeficiency)
 - Chronic (longer than 10 days) or recurrent use of systemic corticosteroids during the study and within 6 months before first administration of study vaccine (*Note:* Ocular, topical or inhaled steroids are allowed)
 - Administration of antineoplastic and immunomodulating agents or radiotherapy during the study and within 6 months before the first administration of study vaccine.
13. Subject has received treatment with immunoglobulins in the 2 months, or blood products in the 4 months before the planned administration of the first dose of study vaccine or has any plans to receive such treatment during the study.
14. Subject is in receipt of, or planning to receive, licensed live attenuated vaccine within 28 days of each study vaccination (ie, before and after); other licensed vaccines (ie, not live: eg, tetanus, hepatitis A, hepatitis B or rabies) should be given at least 14 days before or 14 days after each study vaccination.
15. Subject has received vaccination with seasonal influenza vaccine for the current influenza season in the Northern Hemisphere.
16. Subject has received an investigational drug or used an invasive investigational medical device within 30 days or received an investigational vaccine within 6 months before the planned administration of the first dose of study vaccine or is currently enrolled or plans to participate in another investigational study during the course of this study. *Note:* *Participation in an observational clinical study (ie, with no intervention) is allowed upon approval of the sponsor.*
17. Subject has a contraindication to intramuscular injections and blood draws, eg, bleeding disorders.
18. Any condition for which, in the opinion of the investigator, participation would not be in the best interest of the subject (eg, compromise the well-being) or that could prevent, limit, or confound the protocol-specified assessments.
19. Subject who, in the opinion of the investigator, is unlikely to adhere to the requirements of the study, or are unlikely to complete the full course of vaccination and observation.
20. Subject cannot communicate reliably with the investigator.
21. Subject is an employee of the investigator or study site, with direct involvement in the proposed study or other studies under the direction of that investigator or study site, as well as family members of the employees or the investigator, or an employee of the sponsor.

NOTE: Investigators should ensure that all study enrollment criteria have been met at screening. Section 17.4, Source Documentation, describes the required documentation to support meeting the enrollment criteria.

4.3. Prohibitions and Restrictions

Potential subjects must be willing and able to adhere to the following prohibitions and restrictions during the course of the study to be eligible for participation:

1. Refer to Section 8 regarding prohibited and restricted therapies and vaccines during the study.
2. Agree to follow all requirements that must be met during the study as noted in the inclusion and exclusion criteria (Section 4.1 and Section 4.2, respectively).
3. Vaccination with live attenuated vaccines within 28 days of a study vaccination (ie, before and after) is prohibited. Other vaccines (eg, tetanus, hepatitis A, hepatitis B, rabies) should be given at least 14 days before (or at least 14 days after) administration of study vaccine in order to avoid potential confusion of adverse reactions and potential immune interference. If a vaccine is indicated in a post-exposure setting (eg, rabies or tetanus), it must take priority over the study vaccine.

5. STUDY VACCINE ALLOCATION AND BLINDING

Study Vaccine Allocation

If cellular immune responses are evaluated by the site, subjects will be assigned to two strata prior to randomization, depending on their consent to blood sampling for peripheral blood mononuclear cell (PBMC) assessment and the PBMC sampling capability of the site. The first stratum will contain a maximum of 40 subjects from whom PBMC samples will be collected. The second stratum will contain the remaining subjects, to reach the target of a total of 180 subjects in the study: from these subjects no PBMC samples will be collected. After a maximum of 40 subjects has been assigned to the first stratum, the remaining subjects will be assigned to the second stratum regardless of their PBMC sampling consent. Within each stratum, subject will be randomized 1:1 to one of the two groups. The two strata will be randomized in parallel, depending on the PBMC capability of the site.

If cellular immune responses are not evaluated by the site, then subjects will be randomized 1:1 in one of the two groups.

Randomizations will be based on computer-generated schedules prepared before the study by or under the supervision of the sponsor. The randomizations will be balanced by using randomly permuted blocks.

A unique code will dictate the study vaccine assignment for the subject.

Withdrawal of randomized subjects from vaccination before the first dose: If randomized subjects are withdrawn from vaccination before the first dose is administered, additional subjects may be recruited to replace these subjects at the discretion of the sponsor. Any replacement subject will be assigned to the same group as the original (discontinued) subject. The

replacement subject's randomization number will equal the randomization number of the discontinued subject +1000 (for example subject 0001 would be replaced by subject 1001).

Withdrawal of randomized subjects from vaccination after the first dose (for reasons other than due to an AE): Any randomized subject who is withdrawn from the study for reasons other than due to an AE after the first dose but before the second dose might be replaced at the discretion of the sponsor. Any replacement subject will be assigned to the same group as the original (discontinued) subject. The replacement subject's randomization number will equal the randomization number of the discontinued subject +2000.

Blinding

The investigator will be provided with a sealed randomization code for each subject, containing coded details of study vaccine allocation. All randomization codes, whether opened or sealed, will be collected after the end of the subject's participation in the study.

Unblinding^a will only occur at the time of database lock of the primary analysis. While the responsibility to break the study vaccine allocation code in emergency situations resides solely with the investigator, it is recommended that the investigator contact the sponsor or its designee to discuss the particular situation, before breaking the blind. Telephone contact with the sponsor or its designee will be available 24 hours per day, 7 days per week. In such cases, the investigator may in an emergency determine the identity of the study vaccine by opening the sealed code. In the event the blind is broken, the sponsor must be informed as soon as possible. The date, time and reason for the unblinding must be documented in the appropriate section of the eCRF. The investigator is advised not to reveal the study vaccine assignment to the study-site personnel or sponsor personnel.

The subjects, study-site personnel (including the vaccine administrator) and investigator will be blinded to study vaccine allocation throughout the study, except for the pharmacist or qualified staff member with primary responsibility for study vaccine preparation and dispensing. Note: Only Ad26.RSV.preF administration will be blinded; Fluarix administration will not be blinded.

If the randomization code is broken by the investigator or the study-site personnel, the subject must discontinue further study vaccine administration and must be followed as appropriate (see Section 10.2 for details). If the randomization code is broken by the sponsor for safety reporting purposes, the subject should not discontinue further study vaccine administration and may remain in the study (if the randomization code is still blinded to the study-site personnel and the subject).

^a ie, at the subject level.

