11.4. Immunogenicity Analyses

The **primary immunogenicity objective** is to demonstrate the non-inferiority of the concomitant administration of Ad26.RSV.preF and seasonal influenza vaccine versus the administration of seasonal influenza vaccine alone in terms of humoral immune response expressed by the GMTs of HI antibody titers against all four influenza vaccine strains 28 days after the administration of influenza vaccine, using a non-inferiority margin of 2 for the GMT ratio (Control group/CoAd group).

The primary immunogenicity objective will be assessed by calculating the 95% one-sided upper confidence limit for the difference in log-transformed HI antibody titers for each of the four seasonal influenza vaccine strains between Control and CoAd groups. The confidence limit will be calculated using Welch's t-interval method. The confidence limit will be back-transformed (by exponentiation) to a GMT ratio and compared to the non-inferiority limit of 2.

Only if the 95% one-sided upper confidence limit for the GMT ratio (Control group/CoAd group) of the HI antibody titers lies below 2 for each of the four vaccine strains, non-inferiority of co-administration versus separate administration will be concluded. If one or more confidence limits for the GMT ratio exceed 2, non-inferiority cannot be concluded.

As a sensitivity analysis, the primary endpoint will also be evaluated adjusting for baseline HI levels.

The **secondary and exploratory efficacy endpoints** are listed in Section [2.1](#).

Continuous secondary and exploratory variables will be summarized with descriptive statistics of the actual values and the changes from baseline where appropriate. Descriptive statistics (geometric mean and 95% confidence interval for ELISA, virus neutralization and HI assays; median and quartiles for ELISpot and intracellular cytokine staining [ICS]) will be calculated for continuous immunologic parameters at all timepoints. For the humoral assays, geometric mean

fold rises from baseline and corresponding 95% confidence intervals might additionally be calculated. For immunogenicity, baseline is considered as the last assessment pre-vaccination. Graphical representations of immunologic parameters will be made as applicable.

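### If PBMC sampling is done, randomization is stratified but the primary Welch interval has no stratum term; the analysis is valid and meets its stated power, and adding the term is a small, nearly free gain

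*Protocol*

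**What the plan says.** Stratification is conditional. Protocol Section 5 states: "If cellular immune responses are evaluated by the site, subjects will be assigned to two strata prior to randomization". The PBMC stratum is capped: "The first stratum will contain a maximum of 40 subjects from whom PBMC samples will be collected". Once it is full, "the remaining subjects will be assigned to the second stratum regardless of their PBMC sampling consent". Allocation is then stratified: "Within each stratum, subject will be randomized 1:1 to one of the two groups", and "The randomizations will be balanced by using randomly permuted blocks". In the other branch there is no stratification: "If cellular immune responses are not evaluated by the site, then subjects will be randomized 1:1 in one of the two groups".

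Section 11.4 (repeated in the Synopsis) sets the primary comparison as a one-sided 95% upper limit for the Control-minus-CoAd difference in log HI titer, separately for each of four strains. All four limits must lie below a GMT ratio of 2. On method it says: "The confidence limit will be calculated using Welch's t-interval method". The only covariate named is baseline HI, and only for a sensitivity analysis. Section 11.2 assumes an SD of 2 on the log2 scale, 94.6% power per strain and 86 evaluable subjects per group, with the four strains treated as independent.

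**The concern.** Balancing the groups on a factor takes that factor's contribution out of the true variance of the group difference. An unstratified Welch standard error still contains it. If the factor is related to the titer, the estimated standard error is larger than the true one, the upper limit is pushed towards the margin, and the test runs below its nominal 5%.

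The PBMC stratum could be related to titer. It needs consent to a larger blood draw (60 mL rather than 20 mL per visit, Section 9.1.1). Because it closes at 40 subjects, it may also favour early enrollees. This is plausible only; the protocol gives no data on it.

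At stake is a little precision in a trial that succeeds only if four limits all pass, so that a small per-strain loss compounds. This is a method that Section 11.4 itself fixes, not a detail left open for the SAP.

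**Working it through.** **Inputs from the protocol.** Margin: GMT ratio 2, which is 1.0 on the log2 scale. One-sided 5% per strain. SD 2 log2. 86 evaluable per group. PBMC stratum at most 40 of 180, so p = 40/180 = 0.222 and p(1−p) = 0.1728.

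**Assumptions not in the protocol.** True GMT ratio 1 (needed to reproduce the 86). The SD of 2 is the total SD. The PBMC stratum is full and the groups stay balanced on it among evaluable subjects. The stratum difference d in mean log2 titer is varied over a range.

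**Step 1: the plan's own figure.** 0.80^(1/4) = 0.946, as stated. The SE of the difference is 2 × √(2/86) = 0.3050. Exact noncentral-t power is 94.54% at 85 per group and 94.75% at 86, so 86 is the smallest number that reaches 94.6%. For four independent strains, 0.9475^4 = 80.6%. The plan's figure reproduces for the unadjusted analysis that it specifies.

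**Step 2: standard error.** With the total variance held at 4, the within-stratum variance is 4 − 0.1728 d². The true SE under stratified balance is √(4 − 0.1728 d²) × √(2/86). The Welch SE stays near 0.3050.

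| d (log2) | GMT fold | Within-stratum SD | True SE | Welch SE too wide by |
|---|---|---|---|---|
| 0 | 1.0 | 2.000 | 0.3050 | 0% |
| 0.5 | 1.4 | 1.989 | 0.3033 | 0.5% |
| 1.0 | 2.0 | 1.956 | 0.2983 | 2.2% |
| 1.5 | 2.8 | 1.900 | 0.2898 | 5.2% |

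**Step 3: four-strain power.** The normal approximation with t(0.95, 170) = 1.654 is used. Per strain, Welch power is Φ[(1 − 1.654 × 0.3050)/SE_true] and stratified power is Φ[1/SE_true − 1.654]. Each is raised to the fourth power.

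- At d = 1.0, Welch: Φ(0.4956/0.2983) = Φ(1.661) = 95.2%, and to the fourth power 82.0%.
- At d = 1.0, stratified: Φ(3.352 − 1.654) = Φ(1.698) = 95.5%, and to the fourth power 83.3%.

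| d (log2) | Welch | With stratum | Gain (points) |
|---|---|---|---|
| 0.5 | 81.1% | 81.4% | 0.3 |
| 1.0 | 82.0% | 83.3% | 1.3 |
| 1.5 | 83.7% | 86.3% | 2.6 |

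At d = 0 the two analyses agree apart from one degree of freedom.

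**Step 4: simulation check.** 40,000 trials per setting were run, with 19 of 86 per group in the PBMC stratum.

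| d (log2) | Per-strain power, Welch / stratum | Type I error, Welch / stratum |
|---|---|---|
| 0 | 94.6% / 94.6% | 5.0% / 5.0% |
| 0.5 | 95.0% / 95.1% | 4.9% / 5.0% |
| 1.0 | 95.0% / 95.4% | 4.5% / 4.8% |
| 2.0 | 96.3% / 97.5% | 3.6% / 5.1% |

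Simulation error on the power figures is about 0.1 points. Welch never falls below the planned 94.6%, and its type I error never exceeds 5%.

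**The case against.** The strongest reply is that nothing here is broken. Section 11.2 sizes the trial for an unadjusted comparison with a total SD of 2, Section 11.4 analyses it that way, and the promised power is met at every stratum difference tried. If the strata do differ, Welch power rises above plan, because the true variance falls. The compounding over four strains is already budgeted in the 94.6%, and Section 11.2 notes that correlation between strains may raise overall power. All of this stands.

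The assumption behind the gain is also open to challenge. The stratum is an operational sampling group at a single center, consent is ignored once 40 are in, and the strata are randomized in parallel. A 1.0 log2 difference between people who do and do not give PBMC samples is as large as the non-inferiority margin. This stands too: the gain may be close to zero. Baseline HI, already in the sensitivity analysis, is a more plausible prognostic factor.

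A reader might go further and infer that the plan gives power away for nothing. The documents do not support that. The plain Welch interval is simple, allows unequal variances, matches the sample-size basis and applies unchanged in both branches of Section 5. The shortfall is measured against a slightly better alternative, not against the stated power.

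What survives is narrower. Where the trial does randomize within strata, the primary method that the protocol names does not use them, and using them costs almost nothing.

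**Conclusion.** A minor, optional improvement. If PBMC sampling is done, the primary analysis does not reflect the stratified randomization. The consequence is confined to an interval that is slightly too wide if HI titers differ by stratum: 0.5% at 0.5 log2 and 2.2% at 1.0 log2, or about 0.3 and 1.3 points of four-strain power under independence. With no stratum difference there is no loss.

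The sizes rest on the assumed stratum difference, a true GMT ratio of 1, a total SD of 2 and a full PBMC stratum of 40. A reader might also infer an invalid test or an underpowered trial; neither follows. Type I error is not inflated, the stated power is met, and the required sample size does not change.

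**What to change.** In Section 11.4, and in the matching Synopsis text, specify that the Control-minus-CoAd difference in log HI titer is estimated with the randomization stratum as a factor. Either a linear model with group and stratum and a heteroscedasticity-robust standard error, or a stratum-weighted Welch estimate, keeps the allowance for unequal variances. Add the same term to the baseline-HI-adjusted sensitivity analysis and keep the plain Welch interval as a further sensitivity analysis. State that the term drops out if no PBMC stratum is used.

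Make the change before the unblinded 28-day post-first-dose analysis in Section 11.6, so that the choice of primary method cannot be questioned later. The cost is one sentence in the protocol and SAP, one model term and one degree of freedom, with no extra data and no change in sample size.
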